7.0 Expected Risks/Benefits

1. **Typhoid vaccine:** Mild reactions to the typhoid vaccine may occur, such as fever, headache, redness/swelling at the site of injection, nausea, or muscle pain. You may also faint or an allergic reaction may occur. The risk of serious harm or death is extremely small and serious problems from the typhoid vaccine are very rare. Participants with a history of adverse reactions to the typhoid vaccine, will be removed from the study.
2. **Health information:** Risk of loss of privacy or confidentiality of health information. To minimize the risk, all data will be stored coded.
3. **Questionnaires:** Participants may feel uncomfortable providing personal information in the questionnaires.
4. **Blood pressure:** Blood pressure will be measured using a cuff around the arm. Subjects may feel some discomfort when the cuff is inflated on the arm or may feel some tingling in the fingers.
5. **ECG (Heart rate):** Skin redness may appear where the electrodes are placed on the skin for the ECG.
6. **Pulse wave analysis and Pulse wave velocity:** No known risks.
7. **Ultrasound:** No known risks. All efforts will be made to maintain patient's modesty. The gel used during the ultrasound may feel cool and sticky and is hypoallergenic (not likely to cause an allergic reaction) and washes off easily.

8. **Fasting:** May cause mild discomfort and hunger pains. If participants develop any further symptoms due to fasting, we have snacks and drinks (water and juice) available. Participants will *not* have to perform the treadmill test in the fasted state, reducing risk.
9. **Flow-mediated dilation:** Subjects may feel uncomfortable (i.e. the arm may “fall asleep”) when the blood pressure cuff is inflated for 5 minutes during flow-mediated dilation but this will subside when the cuff is released.
10. **Treadmill test (VO₂max):** The treadmill test may result in muscle soreness, feeling tired, or out of breath. The soreness should go away in a few days. Participants may also feel dizzy, faint, trip, fall, or sprain an ankle during the testing. Spotters will be used during the test. A mouthpiece will be worn to measure breathing so participants may feel uncomfortable. Participants may feel warm during the test. Temperature will be kept at a comfortable temperature between 72-75 degrees Fahrenheit. Additional fans will be provided, as needed, to keep the participant cool and comfortable. Participants will be instructed that they can stop the test at any time. Other rare, but serious, risks associated with a peak exercise test include: rapid or irregular heart rhythms, chest pain, heart attack, and very rarely death. All individuals assisting with the treadmill test are certified in cardiopulmonary resuscitation (CPR) and automated external defibrillator (AED) use. An AED is readily available, as well as a landline phone to call emergency services.
11. **Blood draw:** Subjects may experience mild pain, bleeding or bruising at the site of the blood draw. They may also faint or get a mild infection at the site of the draw.
12. **Near-infrared spectroscopy:** No known risks.
13. **Transcranial Doppler:** Participants may find the headpiece for the brain blood flow measurements uncomfortable and may develop a headache from wearing the head piece over a prolonged period of time (>45 min). The headpiece will be adjusted so that it is as comfortable as possible and the short time frame for wear (<15min) should minimize likelihood of a headache developing.
14. **Cognitive Function Tests:** No known risks.
15. **DEXA:** The DEXA scan involves radiation exposure: The duration of the scan will be less than 10 minutes. You will be exposed to a radiation dose of less than or equal to 0.3 mrem based upon manufacturer’s specifications and pre-determined calculations. This amount of radiation exposure is minimal given the estimated effective equivalent dose is below 100 mrem per year, a limit set by the Nuclear Regulatory Commission for “general public” exposure.
16. **Vitamin C:** There are no known risks associated with the administration of the Vitamin C, as the dosage does not exceed the upper limit for dietary consumption. Additionally, any excess will be excreted out. No side effects have been reported with these doses.

Expected Benefits:

There will be no direct benefit to the subjects for participating in this research.

8.0 Data Collection and Management Procedures

Subject identification will be coded by numerical values. The subject number will be linked to a master key with subject identifiers. The master key, informed consent, health history questionnaires, and documents that provide subject identifiers will be stored separately in a locked cabinet located in the IPL, which is only accessible by key. Only study personnel will have access to this information. During data analyses, shall any abnormalities be discovered regarding the echocardiogram procedure, a letter will be sent to participants suggesting the participant contact their physician for follow-up.

Upon completion of the study, the master key will be destroyed. Subject demographics, such as height, weight, resting HR, and resting BP, will be recorded directly onto a coded data collection form. Data from each subject will be compiled, coded, and saved onto a computer hard drive that is only accessible to study personnel. Electronic data will be stored indefinitely following completion of the study. If the subject agrees to allow us to contact them for future research studies, we will store (by paper and electronically) their name, race, age, sex, height, weight, phone number and email address indefinitely following completion of the study in a separate document.

9.0 Data Analysis

Statistical data analysis will be conducted using IBM SPSS statistical analysis software. This study is a hypothesis generating study, designed to test the anticipated relationship of fitness with aging on vascular function and oxidative stress during an acute bout of inflammation, in generally healthy individuals. This study will provide preliminary data to conduct power analyses for future studies.

10.0 Quality Control and Quality Assurance

All raw data will be checked by [name], as it is collected and all procedures of the protocol will be performed by trained personnel. Biweekly examination of the analyzed data will be performed by [name] to ensure high quality analysis is being performed.

11.0 Data and Safety Monitoring

In the event of an accident or injury occurring during the subject's visit, only emergency care (such as CPR and dialing 911) would be performed by study personnel until emergency medical personnel arrive. No other medical care will be provided. Minor cases, such as subject distress, will be communicated confidentially between the subject and the study personnel. The subject is free to withdraw from the study at any time without affecting future care at UIC. This will be addressed in the informed consent documentation and will be verbally reiterated to the subject on the orientation visit. The informed consent and study personnel will express to the subject the methods by which subject confidentiality will be maintained.

12.0 Statistical Considerations

The data will initially be examined for normality violations, entry errors, and missing values. Entry errors will be corrected by double-checking with original data files. Non-normally distributed data will have an appropriate transformation applied to achieve normality (i.e. log transformation, square root, etc.).

All analyses will be adjusted for age, sex, and body mass index, which are all factors known to influence hemodynamic parameters. Additionally, due to multiple tests, a correction will be applied for multiple comparisons (α divided by the number of tests). Significance level will be set at $\alpha=0.05$, with a Bonferroni correction used to correct for multiple comparisons.

Aim 1: The effects of acute inflammation on endothelial and microvascular function will be tested with a two-way group (3) by time (2) repeated measures ANOVA (V2 and V3 baseline). We expect older high fit adults to have similar vascular reactivity as young adults, i.e. decreased FMD and NIRS reperfusion, suggesting that fitness maintains vascular reactivity during an inflammatory insult with age. If no difference in the response to acute inflammation is seen between low and high fit older adults (not expected), this would indicate fitness is not protective with age during acute inflammation.

Aim 2: The effects of ascorbic acid ingestion will be tested with a two-way group (3) by time (2) repeated measures ANOVA to determine if the antioxidant caused changes at Visit 1 (baseline) or Visit 3 (acute inflammation). A two-way group (3) and time (3) repeated measures (V2 baseline, V3 before and after Vit C) ANOVA will determine if the antioxidant attenuated endothelial function during acute inflammation. At baseline, we expect ascorbic acid to improve vascular function, i.e. increase FMD and NIRS reperfusion, in older low fit adults, with no changes seen in young or high fit older adults. During acute inflammation, we expect ascorbic acid to restore vascular function to baseline in young and older high fit adults. If ascorbic acid does not alter vascular function during acute inflammation, this would indicate another mechanism other than oxidative stress is contributing to vascular dysfunction.

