1.0 Project Summary/Abstract

Acute and chronic inflammation both increase cardiovascular disease risk, especially with aging, which may be due to vascular dysfunction. Aging and inflammation also lead to increased oxidative stress, which impairs vascular function. During acute inflammation, endothelial function is altered differently in younger and older adults with decreases in endothelial function in younger, but not older adults. However, cardiorespiratory fitness is cardio-protective, impacting inflammation, vascular function, and oxidative stress. During acute inflammation, moderately fit older adults exhibit similar responses to younger adults, suggesting preserved endothelial reactivity. However, whether the protective mechanism is oxidative stress has not been confirmed. Furthermore, it is undetermined whether the vascular dysfunction is further propagated down the arterial tree during acute inflammation to the microvasculature. We will investigate these questions through 2 specific aims: 1) To determine if age and fitness moderate the vascular response to acute inflammation; 2) To determine if antioxidant administration eliminates vascular dysfunction during acute inflammation.

We will recruit 15 young low fit (18-35 years) and 30 older low or high fit (55-75 years) adults. An acute inflammatory bout will be induced by typhoid vaccination. The influence of oxidative stress will be assessed using an oral antioxidant. Baseline influences of the antioxidant on endothelial function will be assessed on Visit 1. Acute inflammation measures will be taken at baseline (Visit 2, prior to) and 24-hours after the vaccine (Visit 3). The antioxidant will be administered again on Visit 3.

We anticipate low fit older adults will have reduced endothelial responsiveness and microvascular reactivity compared to young and high fit older adults. Second, we anticipate the antioxidant will improve vascular function at baseline in low fit older adults. During acute inflammation, we anticipate improvement in vascular function to baseline levels in young and older high fit adults.

The results from this study will help to elucidate if fitness is a protective and preventive measure to ameliorate the detrimental cardiovascular response to acute inflammation. Thus, this study may provide health professionals with a behavioral intervention to reduce cardiovascular disease burden in the rapidly growing aging population.

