3.0 Objectives/Aims

Aim 1: To determine if fitness moderates the vascular response to acute inflammation with aging. We hypothesize that during acute inflammation A) high fit older adults will have similar endothelial and microvascular reactivity as young adults; B) high fit older adults will have greater endothelial and microvascular reactivity than low fit older adults.

Aim 2: To determine if antioxidant administration eliminates vascular dysfunction during acute inflammation. We hypothesize A) at baseline, ascorbic acid will improve endothelial function only in low fit older adults; B) during acute inflammation, ascorbic acid will improve vascular function to baseline values in young and older high fit adults.

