4.0 Eligibility

4.1 Inclusion Criteria

- Males and females willing to provide informed consent
- 18-35 or 55-75 years of age
- Non-smoker
- No antioxidant/vitamin supplementation
- No use of anti-inflammatory medication within last 2 weeks
- Aerobically trained (defined as performing aerobic exercise on ≥ 4 days/week, for ≥ 30 minutes, for at least the past 3 months AND a $\text{VO2max} \geq 75^{\text{th}}$ age- and sex-specific percentile according to ACSM)

OR

Sedentary (defined as being involved in less than 30 minutes of moderately-intense physical activity per day, < 3 days/week AND a $\text{VO2max} \leq 50^{\text{th}}$ age- and sex-specific percentile according to ACSM)

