6.0 Study Design and Procedures

Study site

All study procedures except the vaccination will be conducted in the Integrative Physiology Laboratory at the University of Illinois at Chicago located at [name] in the Disability, Health and Social Policy building (DHSP). The typhoid vaccination will be administered by a registered nurse at the Clinical Research Center at UIC.

Design

A comparative, observational study design will be conducted with a group of 15 low fit young adults, 15 low fit older adults, and 15 high fit older adults, for a total of 45 research participants.

Subjects will participate in three study visits, with at least 72 hours between the first two visits, and exactly 24 hours between the last two visits. Menstruating females will be studied during the first 7 days of menses, or during the placebo phase if taking oral contraceptives. Participants will arrive to each visit having refrained from exercise, alcohol, and caffeine for 24h prior to each test day. Participants will be tested in the post-prandial (no food, only water) state (>10 hours) for all visits. (Figure 1)

[figure not shown]

Figure 1. Study protocol schematic

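### Adjusting every analysis for raw age removes most of the information from any comparison that includes the young group, because age is what separates that group from the older ones

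*Combined protocol and SAP*

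**What the plan says.** Section 12.0 (Statistical Considerations) sets one covariate rule for the whole study: "All analyses will be adjusted for age, sex, and body mass index, which are all factors known to influence hemodynamic parameters". The Aim 1 and Aim 2 models that follow are repeated-measures ANOVAs with a three-level group factor. The section does not exempt contrasts with the young group, centre age within group, or say whether covariates are crossed with time.

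Eligibility (section 4.1) is "18-35 or 55-75 years of age". Section 6.0 sets the groups as "15 low fit young adults, 15 low fit older adults, and 15 high fit older adults, for a total of 45 research participants", and section 1.0 assigns the younger band to the first group and the older band to the other two. Nobody aged 36 to 54 is enrolled.

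Several stated expectations depend on the young group:

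- Hypothesis 1A (section 3.0): "high fit older adults will have similar endothelial and microvascular reactivity as young adults".
- Hypothesis 2A (section 3.0): "at baseline, ascorbic acid will improve endothelial function only in low fit older adults".
- The prediction in section 1.0: "We anticipate low fit older adults will have reduced endothelial responsiveness and microvascular reactivity compared to young and high fit older adults".

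Section 9.0 adds: "This study will provide preliminary data to conduct power analyses for future studies".

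**The concern.** Age is not an ordinary confounder between the young and older groups. It is how those groups were defined. If raw age enters beside the group factor, the model estimates an age slope from the spread within each band and carries it across the gap to compare the groups at one common age. With even ages that is (26.5 + 65 + 65)/3 = 52.2 years, which no participant has. The contrast then depends on an extrapolated straight line and inherits the uncertainty of its slope.

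One third of the sample was enrolled for comparisons that this rule leaves very imprecise. Hypothesis 1A adds a risk. It expects similarity and has no equivalence margin, so if the groups truly differ, a much wider interval makes it more likely that the difference is missed and the result read as support. Imprecise young-group estimates could also pass into the future power calculations that section 9.0 foresees.

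**Working it through.** The documents give no power, effect size or standard deviation, so there is no figure of theirs to reproduce.

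**Inputs.** From the documents: n = 15 per group and the age bands 18-35 and 55-75. Assumed: ages uniform within each band, a common age slope, a two-sided test, and a true difference of 1 residual SD.

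**Formula.** With residual variance s², the variance of a young-versus-older contrast is

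- without age: s² × 2/n
- with age: s² × (2/n + D²/SSW)

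D is the difference in mean ages and SSW is the pooled within-group sum of squares of age.

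**Uniform ages.**

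- D = 65 − 26.5 = 38.5.
- SSW = 14 × 17²/12 + 28 × 20²/12 = 337.2 + 933.3 = 1270.5.
- D²/SSW = 1482.25/1270.5 = 1.167.
- Variance ratio = (0.133 + 1.167)/0.133 = 9.75, so the standard error is multiplied by 3.12.
- Equivalent sample size = 15/9.75, about 1.5 people per group.

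**Other age distributions.** Power is from the noncentral t with 39 df.

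| Ages | Variance ratio | SE multiplier | 95% CI half-width (SD) | Power for 1 SD, α = 0.05 |
|---|---|---|---|---|
| No age covariate | 1 | 1 | 0.74 | 76% |
| Most favourable mix the bands allow | 2.97 | 1.7 | 1.27 | 34% |
| Each group split evenly between its two age limits | 3.72 | 1.9 | 1.42 | 28% |
| Uniform over the full bands | 9.75 | 3.1 | 2.31 | 14% |
| Uniform 20-30 and 55-70 | 17.44 | 4.2 | 3.08 | 10% |
| Uniform 25-35 and 55-65 | 20.29 | 4.5 | 3.33 | 9% |

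The most favourable row comes from a search over allocations of participants to their own age limits. It has 14 of 15 young at 35, and 5 of 15 in each older group at 75 with the rest at 55. It keeps 1/2.97 = 34% of the information. At a Bonferroni level of 0.05/3 (assumed, since the number of tests is not stated), power falls from 60% to 6% with uniform ages and to 19% in the most favourable case.

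**Full design.** In 5,000 simulated designs with sex and BMI included and the older groups matched on age, the median variance ratio was 9.7 for both young contrasts (95% of draws about 6.8 to 15.5). It was 1.00 for high-fit versus low-fit older.

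**Change versus level.** Empirical standard errors of a contrast between young and an older group, 2,000 simulations:

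- Change from Visit 2 to Visit 3: 0.356 without age, 0.356 with age as a main effect only, 1.141 with age crossed with time.
- Level at Visit 3: 0.452 without age, 1.400 with age.

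**Power for change, age crossed with time.** In 6,000 simulations of the pattern the plan expects (young and high-fit older fall 1 SD, low-fit older unchanged):

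| Test | Without age | With raw age | Age centred within group |
|---|---|---|---|
| Young vs low-fit older | 74% | 13% | 73% |
| High-fit vs low-fit older | 75% | 75% | not reported |
| Omnibus group-by-time | 77% | 65% | 77% |

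If only the young decline, which is the age pattern section 1.0 describes as "decreases in endothelial function in younger, but not older adults" but with no fitness effect, omnibus power falls from 76% to 10%.

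**The case against.** The best defence is that the planned tests are group-by-time tests. If age enters only as a main effect, change contrasts are untouched. That is correct, and the power losses for change depend on age being crossed with time. But a covariate that cannot act on change does not adjust the group-by-time test, and section 12.0 says every analysis is adjusted. Comparisons of level lose the information under either reading, and hypothesis 1A is worded as reactivity during inflammation.

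Other points are fair and limit the scope:

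- The plan's own reading of Aim 1 turns on low-fit versus high-fit older adults, which is unaffected. Under the expected pattern the omnibus test loses only 12 percentage points. The fall to 10% assumes no fitness effect.
- If 1A is true, a non-significant result has about 95% probability with or without age. The harm arises when 1A is false: with uniform ages the chance of missing a 1-SD difference rises from 24% to 86%. The missing equivalence margin is a separate gap.
- Young versus low-fit older is a prediction in section 1.0, not a numbered hypothesis.
- No Aim 2 model was computed. The word 'only' in hypothesis 2A implies a comparison between groups, but the size there is inferred from the same formula.
- Section 9.0 calls the study hypothesis generating. That explains the absence of a power calculation. It does not justify a covariate that discards most of a planned comparison.

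**Conclusion.** The concern holds. As written, the covariate rule defeats the comparisons that the young group was enrolled for. The loss is about 90% of the information if ages are uniform, and at least 66% for any age mix the eligibility bands allow (taking the older groups alike). This is certain for comparisons of level. For comparisons of change it applies if age is crossed with time, and the plan must say which model is meant. Hypothesis 1B is practically unaffected. The power figures also rest on an assumed 1-SD difference. A further possibility, that the within-band age slope happens to account for the young-older gap and the adjustment removes the ageing effect itself, is not assumed in any of these numbers.

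**What to change.** Amend section 12.0 before analysis:

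- Omit raw age from every model or contrast that includes the young group, or enter it as the deviation from the participant's own group mean.
- Keep sex and BMI, mean-centred.
- Use raw age, or the matched pair from section 5.0, only in the older-only comparison of high-fit with low-fit adults.
- State whether covariates are crossed with time.

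The cost is one or two sentences, with no new data or participants. With uniform ages, the interval for young-group contrasts narrows about threefold compared with the present rule (1.7-fold in the most favourable age mix). The change does not supply the missing equivalence margin for hypothesis 1A.

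### Section 12 applies Bonferroni over an unstated number of tests and then draws conclusions from non-significance, which the correction makes easier to reach

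*Combined protocol and SAP*

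**What the plan says.** Section 12.0 states: "Significance level will be set at $\alpha=0.05$, with a Bonferroni correction used to correct for multiple comparisons". The sentence before it says that "due to multiple tests, a correction will be applied for multiple comparisons" and describes the rule as "α divided by the number of tests". The number of tests is not given, the family is not defined, and no outcome is named primary there or in Sections 3.0 and 9.0.

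The same section plans four ANOVAs per outcome:
- Aim 1: "tested with a two-way group (3) by time (2) repeated measures ANOVA (V2 and V3 baseline").
- Aim 2: two 3-by-2 models "to determine if the antioxidant caused changes at Visit 1 (baseline) or Visit 3 (acute inflammation").
- Aim 2: one 3-by-3 model (Visit 2 baseline, Visit 3 before and after vitamin C).

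The outcomes named in those paragraphs are FMD and NIRS reperfusion. Section 6.0 sets the groups at "15 low fit young adults, 15 low fit older adults, and 15 high fit older adults".

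Hypothesis 1A in Section 3.0 is a similarity claim: "high fit older adults will have similar endothelial and microvascular reactivity as young adults". No margin or equivalence test accompanies it. Two rules in Section 12 draw conclusions from nulls. One begins "If no difference in the response to acute inflammation is seen between low and high fit older adults" and concludes that fitness does not protect. The other concludes that something besides oxidative stress is at work if ascorbic acid produces no change.

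**The concern.** A multiplicity correction guards against false claims of a difference. It does nothing to guard against false claims of no difference, and it makes them more likely, because every additional test in the divisor makes non-significance easier to obtain.

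This plan draws substantive conclusions in both directions. Two null-based conclusions are written out. For hypothesis 1A the plan offers only an ANOVA, so a non-significant difference is the only support it could give. Part of Aim 2 has the same form: no change expected in two groups at baseline, and a return to baseline values under inflammation in hypothesis 2B.

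Because the divisor is unstated, neither the threshold nor the strength of this tilt can be determined before the data are seen.

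**Working it through.** The documents give no power calculation, target difference or FMD standard deviation, so there is no figure to reproduce.

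**Inputs**
- From the documents: 15 per group, 3 groups, alpha 0.05.
- Assumed: two-sided tests, no dropout, and an effect of 1 SD, where SD is that of the quantity compared (for Aim 1, the change from Visit 2 to Visit 3; for paired contrasts, the within-group change). Covariate adjustment is not modelled.

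**Possible divisors k**
- 3: the pairwise group comparisons after one ANOVA.
- 8: FMD and NIRS reperfusion × 4 ANOVAs.
- 12: FMD and the two NIRS measures in the Section 2.0 pilot data × 4 ANOVAs.
- 36: those 12 models × 3 F tests (group, time, interaction).

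Arterial stiffness and blood markers are left out; they would add more.

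**Formulas, each at alpha = 0.05/k**
- Omnibus, one group differing by 1 SD: λ = 15 × [(1/3)² + (1/3)² + (2/3)²] = 15 × 2/3 = 10. Power = P(noncentral F with 2, 42 df and λ = 10 exceeds its critical value).
- One pair of groups: noncentrality = 1 × √(15/2) = 2.74, 42 df. Chance of missing = 1 − power.
- Paired change within a group: noncentrality = √15 = 3.87, 14 df.

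| k | 0.05/k | Omnibus power | Miss a true 1-SD pairwise difference | Paired 1-SD power |
|---|---|---|---|---|
| 1 | 0.0500 | 78% | 24% | 95% |
| 3 | 0.0167 | 63% | 40% | 86% |
| 8 | 0.0063 | 48% | 55% | 73% |
| 12 | 0.0042 | 43% | 60% | 67% |
| 36 | 0.0014 | 29% | 73% | 49% |

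**Nulls without any correction.** At k = 1 the pairwise test misses a true 0.75-SD difference 48% of the time and a true 0.5-SD difference 73% of the time (noncentralities 0.75 × 2.74 and 0.5 × 2.74).

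**Holm against Bonferroni.** Simulation of four contrasts, independent tests, 42 df, 1-SD effects. Bonferroni power per real contrast is about 56%. Holm gives 56% with one real effect, 58% with two, 61% with three and 66% with four, a gain of about 0 to 11 points. At 0.05/4 a true 1-SD difference is still missed about 44% of the time.

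**Precision.** The 95% half-width for a two-group contrast is t(0.975, 28 df) × √(2/15) = 2.048 × 0.365 = 0.75 SD. If the true difference is zero, the whole 95% interval falls inside a margin of ±0.75 SD about 9% of the time, ±1 SD about 51%, and ±1.25 SD about 82%.

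**The case against.** Section 9.0 calls the study hypothesis generating and intends it to supply data for later power analyses, so low power is not itself a breach of its purpose. Bonferroni is valid, and Holm is only a refinement. The sentence about multiple comparisons may mean just the three pairwise comparisons after each ANOVA. In that case power for a 1-SD effect is 63% omnibus and 60% pairwise. Aim 2 rests largely on within-group change, which keeps 86% at k = 3 and 73% at k = 8. The figure of 36 counts main effects that answer no stated hypothesis, and its second NIRS outcome comes from the pilot data.

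Most of this stands as a limit on the size of the problem. A reader might infer that the plan divides alpha by every test and so has only some 30 to 40% power. The documents do not support that, because the divisor is not stated and the effect size is an assumption. Nor do they support saying that most of the power for both aims is lost, given the paired figures.

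The objection does not reach the inferences from null results. An exploratory purpose argues for estimates with intervals; it does not license concluding similarity, lack of protection or another mechanism from a non-significant test.

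**Conclusion.** The point holds. The threshold cannot be determined from the plan, and whichever divisor is chosen, the correction works in favour of the conclusions that rest on non-significance. Over k = 3 to 36, omnibus power is 63% down to 29%, against 78% uncorrected. A true 1-SD difference between young and high fit older adults is missed 40% to 73% of the time, against 24%.

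These figures rest on the assumed 1-SD effect, two-sided tests, complete data and no covariates. Adjusting for age, which nearly separates young from older groups, would further reduce precision for young-versus-older contrasts.

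A reader might infer that naming FMD as sole primary outcome and using Holm would cure both problems. It would not. Holm adds at most about 11 points, and only if all four contrasts are real, whereas hypothesis 1A predicts that one is not. The similarity problem comes from reading a null as evidence, which is unsound even at an uncorrected 0.05.

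**What to change.** In Section 12.0:

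1. List a short family of contrasts tied to hypotheses 1A, 1B, 2A and 2B, and replace Bonferroni with Holm over that family. Holm controls the same error rate and is never less powerful.
2. Delete the rules that infer similarity, lack of fitness protection or another mechanism from a non-significant test. Report each between-group or within-group difference with its 95% interval, labelled as unadjusted. Claim similarity only if that interval lies within a margin set in advance and justified.

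The cost is wording only, with no added participants, visits or measurements. The real downside is that with 15 per group and a half-width near 0.75 SD, the trial will often be unable to claim similarity. That reflects what the data can show.

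Whether NIRS stays in the confirmatory family is the sponsor's choice. Microvascular reactivity is part of both Aim 1 hypotheses, so demoting it is a genuine trade-off, and keeping it lengthens the family.
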